9.4. Key Elements of Analysis Plan

Since this is an 8 week non-inferiority study with two active comparators, the number of withdrawals is expected to be low. In particular, subjects who experience an exacerbation whilst in the study will be allowed to continue participating if possible. Furthermore, the primary comparison is non-inferiority on the per protocol population (a De Jure estimand) and inclusion of data from subjects post-withdrawal would likely bias the results towards a conclusion of non-inferiority. Hence data from subjects post-withdrawal will not be collected. Where possible, data from subjects who withdraw prematurely from the study will be included in any relevant analyses. Specific details for inclusion will be detailed in the RAP, but in general the minimum data required will be a baseline evaluation and at least one on-treatment evaluation. Tipping Point analyses will however be conducted to assess robustness of conclusions. Data collected during a clinic visit will be reported by the visit at which the data were collected and will not be excluded from any analysis for being collected outside of an assessment window.

For the purposes of analyses, a completed subject is defined as anyone completing the last treatment visit for each period (Visit 4 and 7).

It is anticipated that approximately 30 centres (worldwide) will participate in the study. Centres enrolling a small number of subjects may be pooled with another centre. All amalgamations will be finalised and documented in the RAP. These amalgamations will be used wherever region is incorporated into the analysis.

Baseline values for each endpoint will be those used from Visit 1 (screening) or pretreatment in period 1 at Visit 2 (randomisation) or pre-treatment in period 2 at Visit 5 and will be defined in the RAP.

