9.4.1. Efficacy Analyses

All efficacy data will be summarized using means, SDs and ranges for continuous data and frequencies and percentages for categorical data.

Primary Endpoint

The primary endpoint of trough FEV_1 at week 8 will be analysed using a repeated measures model including data recorded at each of Week 4 and Week 8 for the PP population. Treatment group (categorical) will be fitted as the explanatory variable, with period baseline, mean baseline, period, and visit fitted as covariates. Visit (nominal) will be fitted as a categorical variable and visit by period baseline, visit by mean baseline and visit by treatment interaction terms will be included. Treatment effects will be estimated at each visit separately. The variance-covariance matrix will be assumed unstructured. Missing data are not imputed in this analysis; however, all non-missing data will be used within the analysis to estimate the treatment effect at Week 8.

Estimated treatment differences for UMEC/VI vs. TIO/OLO will be presented together with 95% confidence intervals (CIs) for the difference and p-values (for test of superiority).

The MMRM analysis of the primary endpoint will be repeated for the ITT Population testing for superiority in order to ensure consistent results with those from the PP population. These analyses will include data from protocol deviators. In addition, a tipping point analysis will be carried out as a sensitivity analysis for the primary endpoint of trough FEV_1 at Week 8 on the PP and ITT population in order to assess the impact of missing data. Full details will be given in the RAP.

Other Endpoints

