8. OTHER STATISTICAL ANALYSES

8.1. Other Efficacy Endpoints

8.1.1. Overview of Planned Efficacy Analyses

The other efficacy summaries and analyses will be based on the ITT population, unless otherwise specified.

Table 5 provides an overview of the planned efficacy analyses, with further details of data displays being presented in Appendix 13: List of Data Displays.

Endpoint	Change from Baseline[1]						
		Stats Ana	lysis	Summary Indiv		vidual	
	Т	F	L	Т	F	F	L
Responder FEV ₁							
Proportion of	Y			Y			Y
responders according							
to FEV ₁ (a responder is							
defined as a ≥100mL							
change in Trough FEV ₁							
from baseline) at Week							
4 and 8 [2]							
Trough FVC and IC	r	•	1			· · · ·	
Trough FVC	Y	Y		Y			Y
Trough IC	Y	Y		Y			Y
Rescue medication							
Mean number of puffs	Y			Y			Y
per day of rescue over							
the study duration							
(Weeks 1-8) captured							
using e-diary							
Percentage of rescue	Y			Y			Y
free days over the							
study duration (Weeks							
1-8) captured using e-							
diary [2]							
Mean number of				Y			Y
occurrences per day of							
rescue over the study							
duration (Weeks 1-8)							
captured using e-MDI				X			
Percentage of rescue				Y			Y
free days over the							
study duration (Weeks							
1-8) captured using e-							
	N/		T				
CAT score	Y	Y Y		Y			Υ

Table 5Overview of Planned Efficacy Analyses

Endpoint	Change from Baseline[1]							
		Stats Ana	lysis	Sum	mary	Indiv	Individual	
	Т	F	L	Т	F	F	L	
Proportion of CAT	Y			Y			Y	
responders [2]								
Inhaler assessments								
Inhaler ease of use	Y			Y			Y	
Inhaler errors				Y			Y	
E-RS								
E-RS	Y	Y		Y			Y	
Proportion of E-RS	Y			Y			Y	
responders [2]								

NOTES :

- T = Table, F = Figure, L = Listing, Y = Yes display generated.
- Stats Analysis = Represents TFL related to any formal statistical analyses (i.e. modelling) conducted.
- Summary = Represents TFL related to any summaries (i.e. descriptive statistics) of the observed raw data.
- Individual = Represents TFL related to any displays of individual subject observed raw data.
- 1. Analysis and Summaries to include absolute values too for all endpoints with the exception of Responder analysis
- 2. Summary and analysis will be combined into a single display.
- 3. Summary only

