10.3. Appendix 3: Assessment Windows

10.3.1. Definitions of Assessment Windows for Analyses

Data are generally reported according to the nominal time of clinic visits and assessments as specified in the protocol, and time windows for exclusion will not be defined. For example, if a subject recorded values for the Week 4 (Day 28) visit that were actually made on the 21st day of treatment, they will be presented as Week 4 (Day 28) values in the summary tables.

For the 23 and 24 h post-dose trough FEV_1 measurements, a time window of 22.0-25.0 h is allowed for the actual time of an assessment relative to time of dosing on the previous day. Values falling outside of this window will not be used in the PP analysis of the primary endpoint, but will still be included in all ITT analyses.

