10.6.4. Efficacy

Sp	Spirometry		
Tro	bugh		
•	The trough value for FEV ₁ , FVC and IC at each of Week 4 and Week 8 is calculated from the values at the assessments made 23 h and 24 h after dosing on the previous day.		
•	If the actual time of an assessment is after the time of dosing on the current day, the value will not be used in the calculation of trough for the PP population.		
•	For the PP population, a value will additionally be excluded from the trough FEV ₁ calculation if the assessment is outside the time window of 22.0-25.0 h after dosing on the previous day.		
•	If one of the values is missing or excluded then the trough will be the single remaining value; otherwise the trough will be the mean of the two values.		
Pre	oportion of responders according to FEV ₁		
•	A subject will be a considered a responder according to trough FEV ₁ if their trough FEV ₁ value		

- has increased by at least 100mL from baseline.
 A subject will be considered a non-responder if their trough FEV₁ value has decreased, has not changed, or has increased by less than 100mL compared to baseline.
- Missing data will be handled as detailed in Section 10.7.2

Calculation of Daily eDiary endpoints

General

Subjects were instructed to complete the daily eDiary in the evening (typically at bedtime). The parameters collected include rescue use and EXACT-PRO scores.

• The tables below show which daily eDiary records are used to calculate the daily eDiary parameters for each period. Any diary data collected in the post-treatment phase of the study will not be slotted. See Section 10.4.1.1 for details on the assignment of treatment phases.

To be used for rescue medication:

Calculation of Daily eDiary endpoints		
Period	First day	Last day
Period 1 Baseline	Latest of (7 days before Visit 2 (Day 1) and day of Visit 1 (Screening))	Day before Visit 2 (Day 1)
Period 1 Week 1-2	Period study day 1 (day of Visit 2)	Period study day 14
Period 1 Week 3-4	Period study day 15	Period study day 28
Period 1 Week 5-6	Period study day 29	Period study day 42
Period 1 Week 7-8	Period study day 43	Earliest of (Period study day 55 and day before Visit 4)
Period 1 Week 1-8	Period study day 1 (day of Visit 2)	Earliest of (Period study day 55 and day before Visit 4)
Period 2 Baseline	Latest of (7 days before Visit 5 (Day 1) and day of Visit 4)	Day before Visit 5 (Day 1)
Period 2 Week 1-2	Period study day 1 (day of Visit 5)	Period study day 14
Period 2 Week 3-4	Period study day 15	Period study day 28

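### The SAP drops post-dose spirometry from trough only in the PP set, so trough FVC, trough IC and FEV1 responders, analysed only on ITT, can include readings that are not trough

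*SAP*

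**What the plan says.** SAP 10.6.4 states that trough FEV1, FVC and IC at Weeks 4 and 8 "is calculated from the values at the assessments made 23 h and 24 h after dosing on the previous day". Three rules follow.

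- If a reading was actually taken after that day's dose, "the value will not be used in the calculation of trough for the PP population". This bullet is not restricted to FEV1.
- For PP, and for FEV1 only, a reading outside 22.0-25.0 h is also excluded.
- "If one of the values is missing or excluded then the trough will be the single remaining value"; otherwise the two are averaged.

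No other section removes post-dose readings from ITT. Under SAP 10.5.3, planned times are used for derived parameters unless stated otherwise, so a post-dose reading stored in a nominal 23 h or 24 h slot goes into the ITT trough.

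On populations, SAP 8.1.1 says: "The other efficacy summaries and analyses will be based on the ITT population, unless otherwise specified". The display list (SAP 10.13.5, Tables 2.11 and 2.14-2.19) shows FEV1 responders, FVC and IC on ITT, with no PP version. For the ITT repeat of the primary analysis, Protocol 9.4.1 says: "These analyses will include data from protocol deviators".

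**The concern.** A reading after the day's dose captures acute bronchodilation, not the end of the dosing interval. It does not measure the endpoint, whoever is in the analysis set. Because the exclusion is tied to PP while FVC and IC have no PP analysis, the rule as written never acts on any FVC or IC result, although it sits under a definition that covers both. Baseline is treated differently: SAP 10.5.2.1 requires spirometry baselines to be recorded before dosing, with no limit by population. An ITT change from baseline can therefore set a strictly pre-dose baseline against a follow-up mean that is partly post-dose.

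Two uses are at stake. First, under SAP 2.4, p-values for the other lung-function endpoints carry inference if superiority is shown on the primary endpoint. Second, SAP 7.1.1 uses the ITT results as a consistency check on PP and calls for further investigation if they disagree. A difference in how trough is derived should not contribute to such a disagreement.

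**Working it through.** **The plan's own figures, as a yardstick.** Protocol 9.2.1 gives a within-subject SD of 140 mL, a margin of -50 mL, a true difference of 0, one-sided 2.5% and 168 PP subjects.

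- SE = 140 × √(2/168) = 15.28 mL.
- Power = Φ(50/15.28 − 1.96) = Φ(1.31) ≈ 0.905, or 0.902 by the non-central t. This reproduces the stated 90%.
- Observed difference needed for superiority with 186 ITT subjects: t × 140 × √(2/186) = 28.6 mL, which the protocol gives as 29 mL.

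None of these planning figures depends on the ITT trough rule.

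**Is this just the time window again?** No. Suppose that at Week 4 the clinic dose is given 23.5 h after the previous one and the second reading follows at 24 h. That reading lies inside 22.0-25.0 h and is still post-dose. SAP 10.6.4 itself presents the window as a further exclusion, separate from the post-dose one.

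**Where can it occur?** The Time and Events table has an observed clinic dose at Visits 3 and 6 (Week 4), so a late second reading can follow it. Protocol 7.3.1 says no study drug is given at Visits 4 and 7 (Week 8), and Protocol 6.3 has subjects hold the morning dose until staff instruct them. A post-dose reading at Week 8 therefore needs self-dosing against instructions, which would usually affect both readings. The tipping-point analysis uses Week 8 values, so it is exposed mainly by that rarer route.

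**Size.** The documents give neither the acute rise nor the frequency. All values below for the rise d, the share of affected visits f or p, and the net share are assumptions.

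1. *One visit, one of two readings affected.* Shift = d/2. For d = 100-150 mL this is 50-75 mL. A true rise of at least 50 mL (100 − 50) or 25 mL (100 − 75), but below 100 mL, would then be scored as a response.
2. *Mean of one treatment.* Inflation = f × d/2: 0.02 × 100/2 = 1.0 mL; 0.05 × 150/2 = 3.75 mL.
3. *Treatment difference.* Bias = net excess share in one treatment × d × w, with w = 0.5 if one reading is affected and 1 if both are. For d = 50-200 mL and a net share of 1-10%:
   - one reading: from 0.01 × 50 × 0.5 = 0.25 mL to 0.10 × 200 × 0.5 = 10 mL;
   - both readings: from 0.01 × 50 × 1 = 0.5 mL to 0.10 × 200 × 1 = 20 mL;
   - a middle case: 0.02 × 200 × 1 = 4 mL.
4. *Equal shares and equal rises.* There is no bias in the mean difference, only extra variance: SD = √(140² + p(1 − p)d²). For d = 200 mL in both readings, p = 2% gives √(19,600 + 784) = 142.8 mL, and p = 5% gives √(19,600 + 1,900) = 146.6 mL.

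**The case against.** The strongest defence is that the split between ITT and PP is deliberate. Protocol 7.3.1 makes spirometry at Visits 3 and 6 without withholding the morning dose a protocol deviation, and the protocol says that the ITT repeat keeps deviators' data. It also says that visit data "will not be excluded from any analysis for being collected outside of an assessment window". Keeping such readings in ITT and dropping them in PP fits that policy, and the line between a deviation and an invalid measurement is partly a matter of judgement.

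Part of this stands. ITT should keep deviating subjects and off-schedule readings. But the Protocol 9.4 sentence is about windows, and keeping a subject does not require scoring a reading that fails the endpoint's definition. When one reading is dropped, the single-remaining-value rule keeps both subject and visit in ITT.

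A reader might also infer that SAP 10.3.1 expressly keeps post-dose readings in ITT, because it says that certain values "will not be used in the PP analysis of the primary endpoint, but will still be included in all ITT analyses". It does not: those values are the ones outside 22.0-25.0 h, and the section is silent on readings after the current day's dose.

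Two further objections stand. The conduct rules make the event uncommon, especially at Week 8. And removing readings has a side effect: under SAP 10.7.2, a missing post-baseline value with no later assessment counts as non-response, so a careless change could replace a possible false responder at Week 8 with an imposed non-responder.

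**Conclusion.** The point holds as a gap in the derivation of ITT trough. It bears on trough FVC, trough IC and FEV1 responders, for which no planned analysis applies the exclusion, and on the ITT repeat and tipping-point analyses of trough FEV1. Week 4 is the main exposure.

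Three stronger readings are tempting, and the documents do not support them.

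- *That the primary conclusion is at risk.* Non-inferiority and superiority are both tested on PP, where the exclusion applies. The other lung-function p-values carry inference only after superiority is shown there.
- *That the 1-4 mL figure is a bias in the comparison.* It is inflation of one treatment's mean on assumed inputs. Both treatments are LAMA/LABA combinations; with similar frequency and rise, the effect cancels in the mean difference.
- *That the Week 8 responder endpoint is exposed through clinic dosing.* No study drug is given at those visits.

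On the assumed ranges, bias in the ITT difference is likely to be a few mL at most when affected visits are rare. The 20 mL corner needs a 10% net imbalance, a 200 mL rise and both readings affected. For an individual visit, the 50-75 mL shift is material against the 100 mL cut-off. This is a minor point, worth fixing because the fix is simple.

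**What to change.** In SAP 10.6.4, delete the words that limit the post-dose bullet to the PP population, so that it governs trough FEV1, FVC and IC in all populations, judged on actual dosing and assessment times. Leave the 22.0-25.0 h exclusion as a PP-only rule for FEV1.

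Add two sentences: if both readings at a visit are post-dose, trough is missing; and responder status for that visit is then left missing and is not scored as non-response under SAP 10.7.2. Report the number of readings removed by treatment and visit. Add a row to SAP Table 1, because the change narrows the protocol's statement about including deviators' data.

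This is a cheap improvement. The bullet already relies on actual times for PP, so no new data are needed. The downside is that a few ITT trough values become missing; at Week 8 these would be imputed in the tipping-point analysis, over its assumed mean changes of -150 to +150 mL, where they would otherwise have entered as observed. Sample size, power and the primary PP analysis do not change.
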